3.5 Preoperative and intraoperative variables

The preoperative and intra-operative data will be summarised and presented by treatment arm using frequencies and percentages for categorical variables, mean and standard deviation for symmetrical continuous variables, or median and quartiles (25th and 75th percentile) for non-symmetrical continuous variables. If variables have more than 5% missing values, we will report the non-missing sample either in the table or in the footnote of the table. No *p*-values will be reported to compare the two arms with the exception of iron-related variables, i.e. Hb, ferritin, transferrin, and mean corpuscular volume

3.6 Primary outcome

For analysis of DAH90 we will use a Wilcoxon rank sum test, and quantile regression for adjusted treatment effect of the median DAH90 and confidence interval, with the latter considered as the decisive analysis in case of discrepancy. Confidence intervals for the IV iron effect on the median DAH90 or other relevant quantiles will be obtained via bootstrapping with a minimum of B=4000 replicates. The nominal level 95% will be slightly corrected, i.e. 95.4% CI will be used to account for the two interim analyses. Stratification factors will be included as covariates in the quantile regression models.

3.7 Secondary outcomes

Continuous secondary outcomes (#1, 2, 3, 6, 12) will be analysed using multivariable linear regression possibly after transformation. The analysis will be adjusted for the baseline measurement of the outcome where available. Red cell transfusion units (#4), DAH to 30 days (#8) and length of stay outcomes (#7a, 7b) will be summarised with medians and interquartile ranges and with estimated differences between medians and their 95% CIs computed via quantile regression, and for the latter (#7a,b) with death prior to discharge set as the largest duration. Binary outcomes (#4, 5, 9, 10, 11, and safety endpoints) will be expressed as risk ratios and standard 95% CI using log-binomial regression or exact logistic regression to approximate these values when the number of events in either arm is fewer than 5. In case of convergence issues with log-binomial regression, log-poisson regression with robust standard errors will be used. Where possible, adjustment for region, baseline haemoglobin and planned surgery similar to the adjusted analysis for the primary outcome will be carried out in all the models above to be consistent with the primary outcome analysis.

Supplementary analyses of the binary outcomes to 30 days will be performed to take into account the competing risk of death. This will use cumulative incidence functions

with estimated incidence at 30 days, with the incidence compared across treatment groups using risk ratios with 95% CIs derived using the delta method.

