2.3 Randomisation

After consent has been obtained, patients are randomly assigned (1:1) to groups via a web-based service using computer-generated code to either receive IV iron or placebo. Group assignment is stratified by site, baseline haemoglobin (< or \geq 100 g/L), and planned surgery (isolated coronary artery or single valve surgery, or combined/other), using a mix of randomly permuted blocks of different sizes.

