2.7.2 Secondary endpoints

- 1) change in haemoglobin concentration from day of enrolment to day of surgery (preoperative response),
- 2) Correction of iron deficiency state (Δ ferritin, Δ TSat) from treatment to day of surgery
- 3) Change in haemoglobin from day of surgery to 6 weeks post surgery
- 4) Red cell transfusion (any and units) during hospital stay, and post-discharge to 90 days (any).
- 5) Postoperative complications (i.e. MI/stroke/other CVE/infection /thromboembolism) within 30 days of surgery
- 6) 15-item quality of recovery scale on postoperative day 3
- a) Length of stay in hospital (LOS). Hospital stay is calculated from the start (date, time) of surgery until actual hospital discharge or death (in hospital).
 b) ICU stay (hours): ICU stay includes the initial ICU admission and additional time following any ICU readmission up to 30 days after surgery, or death.
- 8) Days alive and at home up to 30 days after surgery (DAH30)
- 9) Disability-free survival, from day of surgery to 6 months after surgery, where disability-free is defined as a WHODAS score <16% at each of 30 days, 90 days and 6 months post surgery.
- 10) Mortality at 30 days, 90 days and 6 months after surgery
- 11) Hospital readmission up to 90 days after surgery
- a) patient-reported quality of life using the MacNew Heart Disease Health-Related Quality of Life Questionnaire (MacNew) up to the day of surgery,
 b) EQ-5D postoperatively at 30 days, 90 days and 6 months after surgery
 c) World Health Organization Disability Assessment Schedule 2.0 (WHODAS) postoperatively at 30 days, 90 days and 6 months after surgery.
- 2.7.3 Safety endpoints (to day 30 post surgery)
 - 1) Anaphylactoid reactions
 - 2) Blood transfusion reactions
 - 3) Cardiovascular events a) MI , b) Stroke)
 - 4) Thromboembolism: as a composite and separated into pulmonary embolism, deep vein thrombosis, Other.
 - 5) Infection a) surgical site, b) deep sternal wound and c) other

6) Adverse events (AE), including the type of AE (neurological, respiratory, gastrointestinal, vascular, renal, skin, musculoskeletal, lymphatic oedema, other [including hypophosphataemia]) and severity (mild, moderate, severe).

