3.1 Analysis principles

• Analyses will be conducted on a modified intention-to-treat (mITT) basis i.e. patients will be analysed according to the treatment they have been originally assigned to provided data is available (treatment policy estimand).

- All tests are two-sided and the nominal level of type I error will be 5%.
- The primary analysis of the effect of treatment on the primary outcome and key secondary endpoints will be adjusted for the stratification factors of baseline haemoglobin and planned surgery, with region adjusted for as a proxy for site to avoid model convergence issues.
- Subgroup analyses will be carried out irrespective of whether there is a significant treatment effect on the primary outcome.
- No imputation of missing values will be carried out for a percentage of missing values less than 5%. When the proportion of missing is substantial (>5%), a sensitivity analysis for the primary endpoint based on inverse probability weighting will be carried out.
- Analyses will be conducted primarily using Stata or R software.

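### The number of red cell units is compared only by a difference in medians, so a fall in units among transfused patients would probably be missed by both planned transfusion analyses

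*SAP*

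**What the plan says.** Section 2.7.2 makes both whether blood was given and how much was given part of endpoint #4: "Red cell transfusion (any and units) during hospital stay, and post-discharge to 90 days (any". Section 3.7 then treats the two parts differently.

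- **Number of units.** Units belong to a group, "Red cell transfusion units (#4), DAH to 30 days (#8) and length of stay outcomes (#7a, 7b", that is summarised by median and IQR and compared through "estimated differences between medians and their 95% CIs computed via quantile regression". No count model or rank test is named for them.
- **Any transfusion.** Endpoint #4 also appears among the yes/no outcomes: "Binary outcomes (#4, 5, 9, 10, 11, and safety endpoints) will be expressed as risk ratios and standard 95% CI using log-binomial regression".

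Both analyses are to be adjusted where feasible ("Where possible, adjustment for region, baseline haemoglobin and planned surgery"). The SAP states no expected transfusion rate and no expected number of units. Section 3.6 fixes a bootstrap interval for DAH90, but section 3.7 does not say how the intervals for the secondary quantile regressions are obtained.

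**The concern.** A difference in medians suits a roughly continuous outcome such as length of stay. Units are whole numbers, mostly small, with many patients tied on each value. The median of such a variable stays put until a cumulative probability crosses one half, and then jumps by a whole unit. A real change in blood use can leave it unmoved, and close to a crossing it can jump by chance.

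Section 2.1 names less transfusion as one route by which iron is expected to help recovery. If iron means fewer units for those who are transfused, without changing how many are transfused, a reported difference of 0 could be taken as no effect on blood use.

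**Working it through.** **Inputs from the SAP.** Allocation 1:1 (2.3); N = 1000 with 5% loss (2.8), so 1000 × 0.95 / 2 = 475 per arm; two-sided 5% level (3.1).

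**Assumed, because the SAP is silent.** Share transfused; negative binomial units with dispersion k; unadjusted percentile-bootstrap interval for the median difference; no crossover.

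**1. The plan's own figure.** There is none for units. The nearest is in section 2.8 for DAH90: 94% power by Wilcoxon, 84% by median regression. The lognormal parameters are not given. With an assumed median stay of 8 days, log-SD 0.7 and crossover out of the iron arm only, simulation gave 93% and 83%. Over median stays of 4-10 days and log-SDs of 0.5-1.1, Wilcoxon power ran from 30% to 100%. The stated pair is therefore attainable but cannot be uniquely reproduced.

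**2. Why the median stalls.** The median is the smallest m with F(m) ≥ 0.5. For a negative binomial with mean μ, P(0) = (1 + μ/k)^(-k) and P(1) = k·μ/(μ + k)·P(0).

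- Control, μ = 2, k = 0.8: P(0) = 3.5^(-0.8) = 0.367; P(1) = 0.8 × 2/2.8 × 0.367 = 0.210; F(1) = 0.577.
- Iron, μ = 1.5 (25% lower): P(0) = 2.875^(-0.8) = 0.430; P(1) = 0.8 × 1.5/2.3 × 0.430 = 0.224; F(1) = 0.654.

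Both medians are 1, so the true difference is 0. The unadjusted estimate was 0 in 299 of 300 simulated trials. With covariates it was 0 in 42, -0.5 in 10 and -1 in 8 of 60.

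Chance jumps: with k = 1 and μ = 4 in both arms (no effect), F(2) = 1 - 0.8³ = 0.488, so each sample median lands on 2 or 3 almost at random. The difference was -1 in 73 and +1 in 63 of 300 trials, so non-zero in 136/300 = 45%.

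**3. Mean units 25% lower** (300 trials per column; power):

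| Zeros in controls | 0.62 | 0.50 | 0.43 | 0.37 | 0.25 | 0.20 |
|---|---|---|---|---|---|---|
| Median-difference interval | 0.00 | 0.02 | 0.02 | 0.00 | 0.14 | 0.06 |
| Any-transfusion risk ratio | 0.41 | 0.37 | 0.56 | 0.48 | 0.56 | 0.51 |
| Wilcoxon | 0.50 | 0.54 | 0.74 | 0.79 | 0.89 | 0.93 |
| Ratio of mean units, robust SE | 0.64 | 0.76 | 0.87 | 0.89 | 0.97 | 0.98 |

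The median does badly even with few zeros, so ties matter as well as zeros.

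**4. Same share transfused, fewer units among the transfused (3.0 v 2.2).** For share p and mean m and variance v among the transfused, CV² = (v + m²)/(p·m²) - 1, and the SE of the log ratio of means is √[(CV²c + CV²t)/475]. Take units given transfusion as 1 + negative binomial with k = 1.5, and p = 0.40:

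- v = 2 + 4/1.5 = 4.67 (control) and 1.2 + 1.44/1.5 = 2.16 (iron).
- CV² = 13.67/3.6 - 1 = 2.80 and 7.00/1.936 - 1 = 2.62.
- SE = √(5.41/475) = 0.107; ln(2.2/3.0) = -0.310; z = 2.91; power = Φ(2.91 - 1.96) = 0.83.

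At p = 0.85 the SE is 0.056, z is 5.54 and power exceeds 0.99. Simulation agrees: 75 / 88 / 96 / 99% at shares of 40 / 50 / 60 / 70% in one run, and 86-100% over 40-85% in another; the gap between the runs is of the size that a different spread produces. The true risk ratio for any transfusion is 1, so that analysis rejects at chance (2-6%). The median interval excluded 0 in 0-5%. At a 50% share the median difference was -1 in 28% of trials and +1 in 27%, so its sign was noise.

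The 0-5% is not a ceiling. With k = 0.8 and p = 0.85, F(1) is 0.15 + 0.85 × 0.367 = 0.462 in controls and 0.15 + 0.85 × 2.5^(-0.8) = 0.558 on iron, on opposite sides of one half. In 300 trials with 300 resamples, the median interval then excluded 0 in 27%, against 100% for the ratio of means.

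**5. Effect only on the share transfused** (10-point fall, units given transfusion unchanged at 1 + negative binomial with mean 1.6, k = 1.5; 2,000 trials):

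| Share transfused | 40 v 30% | 60 v 50% | 70 v 60% |
|---|---|---|---|
| Any-transfusion risk ratio | 90% | 87% | 90% |
| Wilcoxon on units | 88% | 80% | 80% |
| Ratio of mean units | 67% | 59% | 55% |

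In a similar run (500 trials, 300 resamples) the median interval excluded 0 in 0%, 3% and 0%.

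**The case against.** The strongest reply is that the SAP already tests transfusion. A reader might infer from the weak units analysis that a real reduction in transfusion would go undetected. The documents do not support that: section 3.7 plans a risk ratio for any transfusion, and step 5 shows it to be the best of the analyses compared when the share transfused falls by 10 points. It beats the ratio of mean units there by a wide margin. This part of the objection stands, and it confines the point to the number of units.

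A reader might also infer that the estimate can only be 0 or -1. That is too strong: +1 occurs, and the planned covariate adjustment gives fractions such as -0.5. Nor can a high share of zeros be taken as fact. These are anaemic patients having cardiac surgery, the SAP gives no rate, and the share with no transfusion could be low.

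It is also fair that units are one part of one of twelve numbered secondary endpoints, that the planned IQR would show some shift in the upper quartile, and that the poor performance of the median interval rests on a chosen, unadjusted bootstrap. None of this supplies an informative estimate of the effect on units. The IQR is descriptive, and the risk ratio is blind to how much blood each transfused patient receives.

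**Conclusion.** The point holds in limited form. The only planned inference on the number of units is a difference in medians, which is nearly uninformative for a tied count. With 25% fewer mean units and 20-62% zeros in controls, its interval excluded 0 in 0-14% of simulated trials, against 64-98% for a robust ratio of mean units. When iron reduces units only among the transfused (3.0 v 2.2), the figures are 0-5% for the median, 2-6% for the risk ratio and 86-100% for the ratio of means. A wider assumed spread lowers the last figure to 75% at a 40% share, and one favourable configuration raises the median to 27%. All of these rest on assumed negative binomial distributions, 475 per arm and an unadjusted bootstrap. The exact percentages are illustrative; the ordering held in every configuration with an effect on units among the transfused or on mean units. The primary endpoint and the any-transfusion comparison are not affected.

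**What to change.** In section 3.7, take units out of the quantile-regression group. Analyse them by negative binomial or log-linear count regression with robust standard errors, reporting the ratio of mean units with its 95% CI and using the same three covariates as the other secondary models. Leave the any-transfusion risk ratio as planned, and keep the median and IQR of units as description only.

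The cost is a sentence of SAP text and standard code, with no change to design or data. The effect becomes a ratio of means, which a few heavily transfused patients can influence. It also has less power than the risk ratio when only the share transfused changes (55-67% against 87-90% in step 5), so the two should be reported side by side.

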3.8 Handling of missing data

No attempt at weighting or imputing missing outcomes will be attempted if the proportion of missing data is below 5% and missing will be considered missing at random. A complete case analysis will be used as the primary analysis if the potential impact of the missing data is negligible (< 5%). For a proportion of missing data greater than 5%, inverse probability weighting (IPW) where complete cases are weighted by the inverse of their probability of being a complete case [9] will be carried out, with weights determined empirically from variables predictive of missingness. This analysis will be conducted for the primary outcome but will not be systematically undertaken for other endpoints.Patients missing one item in the WHODAS (or EQ-5D) scales at any time point will have the value of the missing item imputed as the mean of the other items. Patients missing two or more items will have their WHODAS (or EQ-5D) set to missing. Patients who died before WHODAS (or EQ-5D) can be measured will have the corresponding endpoint set to missing.

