2.7 Endpoints

2.7.1 Primary endpoint

The primary endpoint, DAH90, is a patient-centred outcome calculated using day and time of surgery as the starting point (Day 0) and calculated thereafter as all days spent at home by the patient until day 90. A few key elements have to be considered to derive this endpoint: 1) a patient who dies within 90 days of surgery is scored as zero irrespective of whether they had spent some of that time at home; 2) in case of hospital readmission after discharge and home return, time spent in hospital due to readmission(s) will be deducted in the DAH90 calculation (up to the limit of 90 days); 3) home is considered to be the patient's normal place of residence or that of a family member, but not a rehabilitation or nursing home facility. This implies that any stay in rehabilitation or nursing home facility within 90 days of surgery will not be classed as "home" in the DAH90 calculation. Examples of DAH90 consistent with this definition are given in the protocol [2

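### SAP 3.8 sets WHODAS-based endpoints to missing after death without exempting disability-free survival (#9), which as written becomes largely a survivors-only comparison

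*SAP*

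**What the plan says.** Section 2.7.2 lists endpoint #9 as "Disability-free survival, from day of surgery to 6 months after surgery". Success requires a WHODAS below the 16% threshold at all three follow-up visits (30 days, 90 days, 6 months). Death is not mentioned in that definition.

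Section 3.7 gives the analysis: "Binary outcomes (#4, 5, 9, 10, 11, and safety endpoints) will be expressed as risk ratios". Each patient therefore needs a yes/no value for #9, or is missing.

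Section 3.8 gives the rule for deaths: "Patients who died before WHODAS (or EQ-5D) can be measured will have the corresponding endpoint set to missing". It does not list the endpoints it covers. The same section treats missing outcomes below 5% as missing at random, and keeps inverse probability weighting for the primary outcome, with no systematic use elsewhere.

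Other endpoints treat death differently. For DAH90 (section 2.7.1), "a patient who dies within 90 days of surgery is scored as zero". For hospital and ICU stay (section 3.7), the analysis is done "with death prior to discharge set as the largest duration".

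**The concern.** Endpoint #9 is built entirely from WHODAS. If death makes the WHODAS-based endpoint missing, a patient who dies on day 60 after a good 30-day score has no value for #9 and drops out of the risk ratio. That patient plainly did not survive free of disability. Death here is a known outcome, not an unobserved score, so a missing-at-random assumption does not fit it.

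At stake is the meaning of a pre-specified, patient-centred secondary endpoint. Leaving out deaths conditions on an event after randomisation. A mortality difference between arms would then be partly or wholly absent from an endpoint whose name says that it includes survival. Two programmers could also derive #9 differently from the same text, and that choice is better settled before unblinding.

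**Working it through.** **Step 1: does any other rule restore death as a failure of #9?**

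- Definition (2.7.2): names survival, but specifies only the WHODAS criterion.
- Missing-data rule (3.8): sets the endpoint to missing after death, with no exception for #9.
- Competing-risk supplement (3.7): "Supplementary analyses of the binary outcomes to 30 days will be performed to take into account the competing risk of death". It stops at 30 days, and #9 runs to 6 months.
- Inverse probability weighting (3.8): not systematic beyond the primary outcome. If it were used, it would reweight patients with data to stand in for those who died; it would not count death as failure.

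None of these repairs the rule.

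**Step 2: who drops out?** A patient who dies before the 30-day assessment has no WHODAS after surgery and always drops out. A patient who dies later drops out only if every score observed so far was below 16%. One observed score of 16% or more already rules out success at all three visits, so that patient can be classed as a failure.

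**Step 3: how many?** The SAP states no 6-month mortality. Its nearest figure is the planning spike of 5% at DAH90 = 0, which section 2.8 attributes essentially to early deaths: 0.05 × 1000 = 50 patients. If 30% to 50% of these had already recorded a failing score (assumed), 50 × 0.70 = 35 to 50 × 0.50 = 25 would drop out. This is a guide only, because the spike concerns 90 days and comes from another trial.

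**Step 4: effect on the risk ratio.** The SAP gives no disability-free rate, so there is no figure to reproduce. Let p be the proportion disability-free at all three visits among survivors, and d the death rate in an arm.

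- Deaths missing: rate = p
- Deaths as failure: rate = p × (1 − d)

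All rates below are assumed.

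| p, iron / placebo | d, iron / placebo | RR, deaths missing | RR, death as failure |
|---|---|---|---|
| 0.60 / 0.60 | 5% / 5% | 1.000 | 0.570/0.570 = 1.000 |
| 0.60 / 0.60 | 3% / 5% | 1.000 | 0.582/0.570 = 1.021 |
| 0.60 / 0.60 | 3% / 7% | 1.000 | 0.582/0.558 = 1.043 |
| 0.60 / 0.60 | 7% / 3% | 1.000 | 0.558/0.582 = 0.959 |
| 0.62 / 0.60 | 7% / 3% | 1.033 | 0.5766/0.582 = 0.991 |

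When p is equal in both arms it cancels from the ratio, so values from 0.50 to 0.70 give the same risk ratios. With equal mortality the ratio is unchanged, but the reported rate is 60% instead of 57%. In the last row the two rules point in opposite directions.

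**Step 5: allowing for failures recorded before death.** If a share f of those who die already count as failures, the rate as written is p(1 − d)/[1 − d(1 − f)]. With p = 0.60, deaths 3% versus 5% and f = 0.5: 0.582/0.985 = 0.591 and 0.570/0.975 = 0.585, so RR = 1.011. This lies about midway between 1.000 and 1.021.

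**Step 6: scale against precision.** With 500 per arm and a 60% rate, SE(log RR) = √(2 × 0.4/0.6/500) = 0.052, so the 95% interval is about ±10%. A shift of 2% to 4% is well inside that.

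**The case against.** The strongest reply is that the sentence in 3.8 was never meant for #9. It pairs WHODAS with EQ-5D, the pair of scores in #12b and #12c; EQ-5D plays no part in #9; and the sentences before it concern missing items in those scales. The word survival in the name of #9 could also be taken at face value, so that a patient who has died has failed. This is a plausible account of the intent. But the SAP does not limit the sentence to #12 and nowhere says that death is a failure of #9, so the text needs correcting on either reading.

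It is also fair that deaths are not hidden in the trial: mortality at 30 days, 90 days and 6 months is endpoint #10, and DAH90 scores death by day 90 as zero. That limits the harm but does not give #9 its stated meaning.

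A reader might infer more than the SAP supports:

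- *That every death, some 50 patients, drops out.* A failing score observed before death can already settle the outcome, and the 5% spike is not a mortality forecast for #9.
- *That the rule always favours the arm with more deaths.* This can happen. If true disability-free survival is 60% in both arms, deaths are 6% versus 3%, and all deaths drop out, the ratio as written is (0.60/0.94)/(0.60/0.97) = 1.03. But that supposes that none of those who died had recorded a failing score. The direction depends on who dies and when.
- *That the item rule for EQ-5D, "will have the value of the missing item imputed as the mean of the other items", is part of the same error.* It is a separate matter, and whether it breaks the score depends on scoring rules that the SAP does not give.

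**Conclusion.** Wrong as written, and a should-fix for one secondary endpoint. Sections 2.7.2, 3.7 and 3.8 taken together make #9 largely a comparison of survivors, against its name and against the scoring of death in DAH90 and length of stay. The plan states a rule that produces the wrong population for this endpoint, so this is more than a missing detail.

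The numerical effect is modest: about 2% on the risk ratio for deaths of 3% versus 5%, about 4% for 3% versus 7%, and less where failures recorded before death are counted. These figures rest wholly on assumed mortality and disability-free rates. The finding itself does not, because it follows from the wording. Nothing here touches the primary analysis of DAH90 or the mortality endpoint #10. The survivors-only treatment of #12b and #12c is openly stated and is not an error; it needs only a label.

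**What to change.** In section 2.7.2 or 3.7, state for #9 that death at any time up to 6 months is a failure; that any observed WHODAS of 16% or more is a failure even if other visits are missing; and that only survivors with no observed failure and an incomplete series are missing.

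In section 3.8, limit the death-to-missing rule to the continuous WHODAS and EQ-5D scores (#12b, c), and label those analyses as survivors only. If the protocol already counts death as a failure of #9, the same edit brings the SAP into line with it.

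The cost is a few sentences of SAP text and a few lines of derivation code. No new data are needed, because death to 6 months is already collected for #10. The change is best made before unblinding and logged under the version tracking in section 1.2.
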